3.0 Patient Eligibility

3.1 Inclusion Criteria

- 3.11 Age ≥ 18 years.
- 3.12 Previously treated ASCT naïve MM patients, currently with relapsed or refractory disease who are being considered for single ASCT for relapsed disease. Patients must be eligible to undergo a stem cell transplant as per institutional criteria for selection at the time of registration.
- 3.13 The following laboratory values obtained ≤ 14 days prior to registration.
- Calculated creatinine clearance (using Cockcroft-Gault equation below)* ≥ 30 mL/min
 - Absolute neutrophil count (ANC) $\geq 1000/\text{mm}^3$
 - Platelet count $\geq 75 \times 10^9/\text{L}$ unless the participant has $\geq 50\%$ bone marrow infiltration in which case a platelet count of $\geq 50 \times 10^9/\text{L}$ is allowed
 - Hemoglobin ≥ 9.0 g/dL
 - Total bilirubin $\leq 1.5 \times$ the upper limit of the normal range (ULN) or if total bilirubin is $> 1.5 \times$ ULN, the direct bilirubin must be ≤ 2.0 mg/dL.
 - Alanine aminotransferase (ALT) and aspartate aminotransferase (AST) $\leq 3 \times$ ULN or $< 5 \times$ ULN if liver involvement

*Cockcroft-Gault Equation:

$$\text{Creatinine clearance for males} = \frac{(140 - \text{age})(\text{actual body weight in kg})}{(72)(\text{serum creatinine in mg/dL})}$$

$$\text{Creatinine clearance for females} = \frac{(140 - \text{age})(\text{actual body weight in kg})(0.85)}{(72)(\text{serum creatinine in mg/dL})}$$

- 3.14 Patients with measurable disease defined as at least one of the following:
- Serum monoclonal protein ≥ 1.0 g/dL by protein electrophoresis
 - ≥ 200 mg of monoclonal protein in the urine on 24-hour electrophoresis
 - Serum immunoglobulin free light chain ≥ 10 mg/dL AND abnormal serum immunoglobulin kappa to lambda free light chain ratio.
- 3.15 ECOG performance status (PS) 0, 1 or 2 ([Appendix I](#)).
- 3.16 Willing to provide informed written consent.
- 3.17 Negative pregnancy test done ≤ 7 days prior to registration, for persons of childbearing potential only.
- 3.18 Willing to follow strict birth control measures.
- Persons of childbearing potential, agree to one of the following:
- Practice 2 effective methods of contraception, at the same time, from the time of signing the informed consent form through 90 days after the last dose of study drug, AND must also adhere to the guidelines of any treatment-specific pregnancy prevention program, if applicable, OR

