 - Agree to practice true abstinence when this is in line with the preferred and usual lifestyle of the subject. (Periodic abstinence [e.g., calendar, ovulation, symptothermal, post-ovulation methods] and withdrawal are not acceptable methods of contraception.)

Persons able to father a child: even if surgically sterilized (i.e., status post-vasectomy), must agree to one of the following:

- Agree to practice effective barrier contraception during the entire study treatment period and through 90 days after the last dose of study drug, OR
- Must also adhere to the guidelines of any treatment-specific pregnancy prevention program, if applicable, OR
- Agree to practice true abstinence when this is in line with the preferred and usual lifestyle of the subject. (Periodic abstinence [e.g., calendar, ovulation, symptothermal, post-ovulation methods] and withdrawal are not acceptable methods of contraception.)

- 3.19a Negative human immunodeficiency virus (HIV), hepatitis B and C test.
- 3.19b Willing to follow the requirements of the Pomalyst REMS program.
- 3.19c Willing to return to enrolling institution for follow-up (during the Active Monitoring Phase of the study).
- 3.19d Willing to provide bone marrow samples under IRB#521-93 for correlative research purposes (see Sections 6.2 and 14.0).

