3.2 Exclusion Criteria

- 3.21 Diagnosed or treated for another malignancy ≤ 2 years prior to registration or previously diagnosed with another malignancy and have any evidence of residual disease.
NOTE: If there is a history or prior malignancy, patient must not be receiving other specific treatment for their cancer. Patients with non-melanoma skin cancer or carcinoma in situ of any type, or low-risk prostate cancer after curative therapy, are not excluded if they have undergone complete resection.
NOTE: Platelet transfusions to help patients meet eligibility criteria are not allowed ≤ 3 days prior to study registration.
- 3.22 Any of the following because this study involves an investigational agent whose genotoxic, mutagenic and teratogenic effects on the developing fetus and newborn are unknown:
 - Pregnant persons
 - Nursing persons
 - Persons of childbearing potential who are unwilling to employ adequate contraception
- 3.23 Co-morbid systemic illnesses or other severe concurrent disease which, in the judgment of the investigator, would make the patient inappropriate for entry into this study or interfere significantly with the proper assessment of safety and toxicity of the prescribed regimens. **NOTE:** this includes uncompensated heart or lung disease.
- 3.24 Receiving any other investigational agent which would be considered as a treatment for the primary neoplasm. **NOTE:** Bisphosphonates are considered to be supportive care rather than therapy and are allowed while on protocol treatment.
- 3.25 Patient has \geq Grade 2 peripheral neuropathy, or Grade 1 with pain on clinical examination during the screening period.

- 3.26 Major surgery ≤ 14 days prior to registration.
- 3.27 Systemic treatment with strong CYP3A inducers (rifampin, rifapentine, rifabutin, carbamazepine, phenytoin, phenobarbital) or use of Ginkgo biloba or St. John's wort ≤ 14 days prior to registration.
- 3.28 Uncontrolled intercurrent illness including, but not limited to, ongoing or active infection, symptomatic congestive heart failure, unstable angina pectoris, cardiac arrhythmia, or psychiatric illness/social situations that would limit compliance with study requirements. **NOTE:** Any ECG abnormality at screening must be documented by the investigator as not medically relevant.
- 3.29a QTc > 470 milliseconds (msec) on a 12-lead ECG obtained during the Screening period.

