10.5 Other Required Reporting

10.51 Unanticipated Problems Involving Risks to Subjects or Others (UPIRTSOS) in general, include any incident, experience, or outcome that meets **all** of the following criteria:

1. Unexpected (in terms of nature, severity, or frequency) given (a) the research procedures that are described in the protocol-related documents, such as the IRB-approved research protocol and informed consent document; and (b) the characteristics of the subject population being studied;
2. Related or possibly related to participation in the research (in this guidance document, possibly related means there is a reasonable possibility that the incident, experience, or outcome may have been caused by the procedures involved in the research); and
3. Suggests that the research places subjects or others at a greater risk of harm (including physical, psychological, economic, or social harm) than was previously known or recognized.

Some unanticipated problems involve social or economic harm instead of the physical or psychological harm associated with adverse events. In other cases, unanticipated problems place subjects or others at increased *risk* of harm, but no harm occurs.

Note: If there is no language in the protocol indicating that pregnancy is not considered an adverse experience for this trial, and if the consent form does not indicate that subjects should not get pregnant/impregnate others, then any pregnancy in a subject/patient or a male patient's partner (spontaneously reported) which occurs during the study or within 120 days of completing the study should be reported as a UPIRTSO.

Mayo Clinic Cancer Center (MCCC) Institutions:

If the event meets the criteria for IRB submission as a Reportable Event/UPIRTSO, provide the Reportable Event coversheet and appropriate documentation and use the Mayo Clinic Cancer Center Expedited Event Report form <http://livecycle2.mayo.edu/workspace/?startEndpoint=MC4158-56/Processes/MC4158-56-Process.MC4158-56>, to submit to [contact]. The Mayo Regulatory Affairs Office will review and process the submission to the Mayo Clinic IRB.

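### Criterion 3.18 lets persons able to father a child choose between 90-day barrier contraception and pregnancy-prevention-program adherence (OR), where the parallel list requires both (AND)

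*Combined protocol and SAP*

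**What the plan says.** Criterion 3.18 (section 3.1, Inclusion Criteria) has two lists.

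- **Persons of childbearing potential.** The first option is two contraceptive methods to 90 days past the last dose, and the same bullet continues "AND must also adhere to the guidelines of any treatment-specific pregnancy prevention program, if applicable, OR". The only alternative is true abstinence.
- **Persons able to father a child.** The stem is "even if surgically sterilized (i.e., status post-vasectomy), must agree to one of the following". Three separate bullets follow. The first is "Agree to practice effective barrier contraception during the entire study treatment period and through 90 days after the last dose of study drug, OR". The second is "Must also adhere to the guidelines of any treatment-specific pregnancy prevention program, if applicable, OR". The third is true abstinence.

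Criterion 3.19b then applies to everyone: "Willing to follow the requirements of the Pomalyst REMS program". Footnote 12 of the test schedule (section 4.1) likewise makes registration in that program mandatory for all participants.

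**The concern.** The two lists appear meant to impose the same structure: contraception plus program adherence, or abstinence. In the second list the connector is OR and the stem asks for one item only, so program adherence becomes a substitute for barrier contraception. Since every patient has to accept the Pomalyst REMS anyway, the substitute is always met, and the 90-day barrier duty obliges nobody who prefers not to take it on.

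What is at stake is a precaution for partners and any pregnancy. Section 3.22 gives as its reason for excluding certain patients that "this study involves an investigational agent whose genotoxic, mutagenic and teratogenic effects on the developing fetus and newborn are unknown". Criterion 3.18 is the one place in the public text where men are given a contraception period counted to 90 days after the last study drug, and its wording makes that period optional.

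**Working it through.** The plan states no figure to reproduce. The check is one of logic, followed by a search for a clause that restores the duty.

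**Step 1: the rule as written.** Let B = contraception to 90 days past the last dose (two methods in the first list, barrier in the second), P = adherence to the pregnancy prevention program, A = true abstinence.

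| List in 3.18 | Rule |
|---|---|
| Childbearing potential | (B AND P) OR A |
| Able to father a child | B OR P OR A |

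**Step 2: a man who is not abstinent.** A is false. Criterion 3.19b makes P true for every enrolled patient. The rule as written, B OR P OR A, is then true whatever the value of B. Under the structure of the parallel list, (B AND P) OR A, it is true only if B is true. The connector alone decides whether the 90-day commitment binds.

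**Step 3: which connector was meant.** The second bullet says the man must *also* adhere. In a free-standing alternative that word has nothing to add to. In the childbearing list the same clause follows AND. The document's own wording therefore points to AND.

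**Step 4: does another section restore 90 days for men?**

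- Section 3.22 excludes "Persons of childbearing potential who are unwilling to employ adequate contraception"; it does not mention persons able to father a child.
- Section 10.51 has a clause on partner pregnancy "which occurs during the study or within 120 days of completing the study should be reported as a UPIRTSO". It applies only if protocol and consent wording on pregnancy is absent, and it governs reporting, not contraception.
- Section 10.551 covers the reporting of partner pregnancies during the man's participation. It sets no contraception duty.
- Section 15.292 (pomalidomide nursing guidelines) is the nearest backstop. It tells sexually active men to use the protocol's contraception while on protocol and for 4 weeks after the agent stops. It names no method and gives no 90-day period.

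**Step 5: days after the last study drug left uncovered, by reading of 15.292.** Maintenance is ixazomib alone (section 7.2), so pomalidomide may stop long before the last study drug.

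| Reading of 15.292 | Uncovered days, out of 90 |
|---|---|
| On protocol includes event monitoring (section 4.2: up to 3 years after registration) | can be 0 |
| On protocol means treatment; the 4 weeks run from the last study drug | 90 − 28 = 62 |
| On protocol means treatment; the agent is pomalidomide and its 4 weeks lapse during ixazomib maintenance | 90 − 0 = 90 |

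The text does not settle which reading applies, so the range is 0 to 90 days.

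**The case against.** The case for leaving this alone has several parts.

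- **The opening line of 3.18** asks for willingness to follow strict birth control measures, and a man refusing contraception hardly fits it. That is fair as to intent, but the line fixes neither method nor duration; the bullets do that.
- **The program bullet carries an if-applicable condition.** Once pomalidomide ends, it could be said to fall away, leaving barrier or abstinence. This is arguable. However, eligibility is judged at registration, when pomalidomide is about to start and the program does apply.
- **Section 15.292 covers treatment.** On its natural reading it does, and barrier is the only contraceptive method that 3.18 names for men. This stands for the treatment period. It does not supply 90 days afterwards.
- **Unseen text may hold the duty.** The REMS terms, Appendix IV (cited in section 7.5) and the consent form are not in the public text. This stands in full. It limits what can be said about consequences, though not about the wording of 3.18.

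A reader might infer two stronger claims. One is a firm 62-day gap; that needs the middle reading of 15.292 in the table above, and the others give 0 or 90. The other is a paternal risk from ixazomib. Section 15.15 gives a mean terminal half-life of 9.5 days, so 28/9.5 = 2.9 half-lives pass in 4 weeks, leaving 2^(−28/9.5) ≈ 13%, against 90/9.5 = 9.5 half-lives and about 0.14% at 90 days. Those are plasma figures that assume simple exponential decline. The documents give no semen or male reproductive data for ixazomib, section 1.3 reports a negative Ames assay, and the exclusions in 3.22 concern pregnant, nursing and childbearing persons. The arithmetic does not establish a risk through the father.

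**Conclusion.** The connector in the second list of 3.18 is wrong as written. The mismatch with the parallel list, the word *also* and the universal REMS criterion in 3.19b establish this from the text alone. As drafted, a non-abstinent man is eligible without committing to barrier contraception for 90 days after the last dose, and no other section of the public text gives him that period.

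The practical effect cannot be given a firm size. It lies between 0 and 90 days depending on the reading of 15.292, and may be nil if the REMS terms, Appendix IV or the consent form already impose the duty. The number of men affected is unknown: section 16.6 expects 17 of 25 patients to be male, but that is only a remote ceiling given the median age at onset of 65–70 years in section 1.1. Many investigators will apply the intended meaning. This is a minor correction to safety wording, with no bearing on the PFS18 endpoint, the 14-of-21 decision rule or any analysis.

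**What to change.** In 3.18, for persons able to father a child, merge the first two bullets into one. Keep the barrier text as far as the 90-day period, drop its closing OR, and continue with the clause already used in the other list: "AND must also adhere to the guidelines of any treatment-specific pregnancy prevention program, if applicable, OR". Leave the abstinence bullet unchanged. Then check that the consent form says the same.

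The cost is one connector and one consistency check. Sample size, accrual, endpoint and analysis stay as they are.

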3.2 Exclusion Criteria

- 3.21 Diagnosed or treated for another malignancy ≤ 2 years prior to registration or previously diagnosed with another malignancy and have any evidence of residual disease.
NOTE: If there is a history or prior malignancy, patient must not be receiving other specific treatment for their cancer. Patients with non-melanoma skin cancer or carcinoma in situ of any type, or low-risk prostate cancer after curative therapy, are not excluded if they have undergone complete resection.
NOTE: Platelet transfusions to help patients meet eligibility criteria are not allowed ≤ 3 days prior to study registration.
- 3.22 Any of the following because this study involves an investigational agent whose genotoxic, mutagenic and teratogenic effects on the developing fetus and newborn are unknown:
 - Pregnant persons
 - Nursing persons
 - Persons of childbearing potential who are unwilling to employ adequate contraception
- 3.23 Co-morbid systemic illnesses or other severe concurrent disease which, in the judgment of the investigator, would make the patient inappropriate for entry into this study or interfere significantly with the proper assessment of safety and toxicity of the prescribed regimens. **NOTE:** this includes uncompensated heart or lung disease.
- 3.24 Receiving any other investigational agent which would be considered as a treatment for the primary neoplasm. **NOTE:** Bisphosphonates are considered to be supportive care rather than therapy and are allowed while on protocol treatment.
- 3.25 Patient has \geq Grade 2 peripheral neuropathy, or Grade 1 with pain on clinical examination during the screening period.

- 3.26 Major surgery ≤ 14 days prior to registration.
- 3.27 Systemic treatment with strong CYP3A inducers (rifampin, rifapentine, rifabutin, carbamazepine, phenytoin, phenobarbital) or use of Ginkgo biloba or St. John's wort ≤ 14 days prior to registration.
- 3.28 Uncontrolled intercurrent illness including, but not limited to, ongoing or active infection, symptomatic congestive heart failure, unstable angina pectoris, cardiac arrhythmia, or psychiatric illness/social situations that would limit compliance with study requirements. **NOTE:** Any ECG abnormality at screening must be documented by the investigator as not medically relevant.
- 3.29a QTc > 470 milliseconds (msec) on a 12-lead ECG obtained during the Screening period.
Note: If a machine reading is above this value, the ECG should be reviewed by a qualified reader and confirmed on a subsequent ECG.
- 3.29b Known allergy to any of the study medications, their analogues or excipients in the various formulations.
- 3.29c Known GI disease or GI procedure that could interfere with the oral absorption or tolerance of study treatment including difficulty swallowing.
- 3.29d Diarrhea $> \text{Grade } 1$, based on the NCI CTCAE v 4.0 grading, in the absence of anti-diarrheals.
- 3.29e Failure to have fully recovered (ie, $\leq \text{Grade } 1$ toxicity) from the reversible effects of prior chemotherapy.
- 3.29f Radiotherapy ≤ 14 days prior to registration.
NOTE: If the involved field is small, 7 days will be considered a sufficient interval between treatment and administration of the ixazomib.
- 3.29g Central nervous system involvement with disease under study (myeloma), or concurrent AL amyloidosis or plasma cell leukemia.
- 3.29h Patients that have previously been treated with ixazomib, or participated in a study with ixazomib whether treated with ixazomib or not.
- 3.29i Prior stem cell transplantation for myeloma

4.0 Study Calendars

4.1 Test Schedule (excluding routine investigations in the peri-ASCT period*)

Tests and procedures	Prior to Registration		Induction and consolidation ^{16,1}	Every cycle pre-treatment including maintenance ^{1,7}	End of Cycle 4 of induction, post ASCT between Day 60-120, end of consolidation and 1 year post initiation of maintenance ^{1,14}	End of Treatment (±14 days) ¹
	≤30 days	≤14 days				
Complete medical history	X				X	
Adverse Event monitoring		X		X	X	X
Physical exam, including weight and vital signs		X		X	X	X
Height		X			X	
Performance status (ECOG scale)		X		X	X	X
Serum pregnancy test		X ¹¹				
CBC with differential		X	X ¹⁵	X ¹⁵	X	X
Chemistry group: sodium, potassium, glucose, alkaline phosphatase; total and direct bilirubin; SGOT (AST); SGPT (ALT), serum creatinine, calcium		X		X	X	X
HIV, hepatitis B and C	X					
LDH, Beta ₂ -microglobulin, C-reactive protein	X				X	
Electrophoresis of serum and urine (SPEP/UPEP)		X		X ³	X	X ³
Affected immunoglobulin ²		X		X ²	X	X ²
Immunofixation serum and urine	X			X ⁴	X	X ⁴
Immunoglobulin free light chain (MML panel)		X		X ⁵	X	X ⁵
ECG	X					
X-ray skeletal survey or whole-body low-dose CT	X			X ⁶	X ⁶	X
CT Scan, PET/CT, or MRI for measurement if evidence of prior EMD lesion ⁸	X			X ⁸	X ⁸	
Circulating plasma cell assessment (flow cytometry or peripheral smear) ⁹		X		X ⁹	X ⁹	
Bone marrow aspirate and biopsy for myeloma ¹⁷	X			X ¹⁰	X ¹⁰	X

Tests and procedures	Prior to Registration		Induction and consolidation ^{16,1}	Every cycle pre-treatment including maintenance ^{1,7}	End of Cycle 4 of induction, post ASCT between Day 60-120, end of consolidation and 1 year post initiation of maintenance ^{1,14}	End of Treatment (± 14 days) ¹
	≤ 30 days	≤ 14 days				
Chest x-ray	X					
Register patient for POMALYST REMS TM program		X ¹²				
Patient Medication Diary (Appendix II) ¹³				X	X	X
Mandatory Research Bone marrow sample ¹⁸	X ¹⁴				X ¹⁴	

*Performed per institutional guidelines. Melphalan conditioning followed by stem cell infusion is being considered as ‘cycle 5’ in the protocol for logistical reasons only. No additional toxicity data will be collected in the immediate post ASCT period until day 60-100 when the patient returns for routine post-ASCT reevaluation.

- 1) All scheduled visits are while patient is receiving therapy will have a window of ± 7 days unless otherwise stated.
- 2) Affected immunoglobulin refers to the baseline M-protein type, that is, IgG, IgA, or IgD. Not applicable if patient “non-secretory” or if patient has no heavy chain, i.e. light chain myeloma. Affected immunoglobulin is required after baseline only if it used for disease monitoring instead of SPEP (e.g. IgA myeloma).
- 3) Urine Electrophoresis required only if used to assess disease response.
- 4) Immunofixation (IF) needed only in the absence of M-protein to document sCR or CR.
- 5) Serial light chain required if it is used for disease monitoring (measurable disease at baseline)
- 6) Every 365 days (12 months) or more often if clinically indicated.
- 7) Does not need to be repeated at Cycle 1 Day 1. Baseline values can be used for cycle 1.
- 8) This test is not mandatory. CT or MRI or the CT portion of the PET/CT, same modality should be used at baseline and for serial evaluation. PET/CT scans are required at baseline for all patients with suspected extra-medullary disease (EMD). Assessment of EMD lesions should be performed at end of induction, post ASCT (range:day 60-120), post consolidation (if persistent EMD noted previously) and every year on maintenance or more frequently if clinically indicated. For patients with only skin involvement, skin lesions should be measured with a ruler with images maintained in the medical record.
- 9) Number of circulating cells may be measured using flow cytometry or peripheral smear as is the standard practice for the institution, but same methodology should be used at every time point. This should be repeated after Cycle 1 and every 2 cycles after that or more often if clinically indicated.
- 10) At the end of 4 cycles and only required to document CR after that and assess MRD. If a bone marrow was done to confirm CR prior to end of 4 cycles, no further bone marrow examination until the end of the phase (induction/~ day 100 post –ASCT, consolidation and annually while on maintenance if CR suspected).
- 11) For persons of childbearing potential only. Must be done ≤ 7 days prior to registration.

- 12) All study participants must be registered into the mandatory POMALYST REMS™ program, and be willing and able to comply with the requirements of the POMALYST REMS™ program.

FOOTNOTES CONTINUE ON NEXT PAGE

- 13) The diary must begin the day the patient starts taking the medication and must be completed per protocol and returned to the treating institution.
- 14) At baseline, end of the phase induction, ~ Day 100 post ASCT, end of consolidation, and 1 year after initiation of maintenance while on maintenance. See [Section 14.0](#).
- 15) Can be performed at an outside facility
- 16) Induction Day 8, 15, 22 (Cycles 1-3), Day 15 (Cycle 4); consolidation Day 8, 15, 22 (Cycles 6-8), Day 15 (Cycle 9)
- 17) The following testing may be done if clinically indicated: Myeloma FISH, plasma cell proliferation, and flow cytometry (MRD).
- 18) Research blood and bone marrow collection per protocol IRB 521-93 will be done after consenting for 521-93 and according to that protocol. All processing will be done on Stabile 6.

